A strategy to improve outcome is dose escalation to the cancer lesions in the prostate. The FLAME randomised trial (NCT01168479) demonstrated improved biochemical control, reduced local failure (LF) and reduced regional + distant metastatic failure (8,28). Toxicity is the limiting factor, and the boost dose was strictly limited depending on organ at risk exposure (OAR) in the FLAME trial. A dose response analysis for biochemical control indicated that patients with higher achieved boost doses experienced better tumour control (29). At the same time, the data suggested reduced toxicity as a result of further consideration of radiation dose to OARs and improved urethral sparing in particular (30). The question is therefore whether the addition of a focal boost can be established as standard of care.

A study larger than FLAME is needed in order to confirm effectiveness with freedom from distant metastases (FFDM) as an improved primary endpoint, compared to biochemical control which was used as primary endpoint in FLAME. However, while endpoints based on biochemical relapse free

survival are not surrogate for overall survival in localised prostate cancer, FFDM is now shown to be a valid surrogate endpoint for OS in trials of localised prostate cancer (31-33). Biochemical control is used as a secondary endpoint in the current study to confirm the FLAME results and study heterogeneity of treatment effects as detailed in the statistics section.

Shortening of treatment duration

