Primary endpoints and dimensioning

Superiority trial: Effect of focal boost

Primary endpoint will be freedom from distant metastasis (FFDM), which is concluded to be a strong surrogate of OS in localised PCa (32). The reference level for FFDM is a challenging parameter to address as it should be expected to improve with recent advances in the adjuvant systemic treatments. However, the population of this study is the highest risk RT patients, and we should therefore expect a distant metastasis (DM) rate that is on average higher than in other trial populations. The FLAME trial reported a DM rate of approximately 11% at 78 Gy dose to the primary target (Data supplement in FLAME). The current trial has a higher risk profile in patient uptake. We thus assume a 10% DM rate (90% FFDM) as a conservative reference level at 5 years, but with sensitivity analysis down to 85% FFDM. Furthermore, a single sided alpha of 5% is used to assess the alternative hypothesis that the boost arms have a FFDM rate at five years of 95% or better. We will assume 5 years uniform accrual plus 1-year additional follow-up (32). This primary sample size assessment yields the need for 254 patients in each of the four arms for a total of 1,016 patients to reach a power of 80% for the one-sided test for superiority on FFDM. The power after an additional 4 years of follow-up under the same assumptions increases to 96%.

Sensitivity analyses for the less conservative power calculations assume 85% FFDM and yield a power of 91% after 5+1 years and 99% after 5+5 years with the same number of patients and relative risk.

Non-inferiority of short fractionation

Defining boundaries of non-inferiority at 15% for GI events and 27% of GU events we have >80% power to detect inferiority with 1,016 patients on both endpoints.

Conclusion

In conclusion, 4x254 patients is a realistic sample size from a recruitment perspective. It is also sufficient to have an impact on guidelines for future patients if the trial is successful.

Secondary endpoints with formal power assessment

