- Dose constraints for organs at risk are kept according to guidelines in this protocol
- Guidelines for IGRT according to institutional protocol.
- Treatment is delivered with institutional protocols that fulfil the goals and constraints given in this protocol (appendix B).

Radiotherapy

Radiotherapy planning:

Modern RT planning is wholly dependent on high level computing. This allows for creation of highly personalised dose plans with several different dose levels within the same plan. Additionally, these plans exhibit sharp dose gradients towards critical organs at risk (OAR). Depending on treatment modality plans will either use a simultaneously integrated or sequential boost. In the former case the treatment session delivers a boost to the intraprostatic lesion (if randomised for boost) in addition to the prescribed doses to prostate and elective targets. In the latter case prescribed doses to prostate and elective targets are delivered in the same treatment sessions whereas a boost will be delivered in separate sessions using specialised equipment e.g. an MR-Linac. In either case the dose planning will seek to minimise the trade-off between sufficient target coverage - usually between 95% and 107% of the prescribed target doses - and reducing as much as possible the doses to OAR. It is not uncommon that requirements for target and OAR doses are mutually exclusive. The order in which every dose requirement should be prioritised is detailed in Appendix B as well as specific

requirements to target coverage. To ensure that the dose planning of all participating centres will be vetted as part of the comprehensive RT-QA program described in Appendix A.

Rectal and bladder preparation protocol:

Patients should be treated with a comfortably filled bladder and an empty rectum/bowel according to local protocol. Use of Image Guided Radiotherapy (IGRT) is mandatory to ensure the elective target coverage and to assess bladder- and rectal filling. Application of a bladder-filling protocol in an attempt to decrease the volume of bladder irradiated is recommended using IGRT to check the target positioning.

Target volume definition, dose and fractionation:

Delineation of the targets are performed on the treatment planning MRI, guided by both the diagnostic multiparametric MRI (mpMRI) and PSMA-PET CT scan. Organs at risk (OARs) are delineated on the planning CT scan.

Fractionation:

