- 20 fractions, no boost: Prostate and seminal vesicles: 60 Gy/ 20 fractions. Pelvic: 45 Gy /20 fractions.
- 20 fractions, boost: Boost 75 Gy/20 fractions, prostate and seminal vesicles: 60 Gy/ 20 fractions. Pelvic: 45 Gy /20 fractions.
 - If a boost is delivered on special equipment, such as an MR accelerator, it is allowed to give the boost in fewer fractions with same equivalent dose and maintaining same overall treatment time
- 12 fractions, no boost: Prostate and seminal vesicles: 50 Gy/ 12 fractions, Pelvic: 37 Gy /12 fractions.
- 12 fractions, boost: Boost 60 Gy/12 fractions, prostate and seminal vesicles: 50 Gy/12 fractions, Pelvic: 37 Gy /12 fractions.
 - If a boost is delivered on special equipment, such as an MR accelerator, it is allowed to give the boost in fewer fractions with same equivalent dose and maintaining same overall treatment time

All treatments with 5 fractions per week

Intraprostatic lesion(s): If a boost is to be performed, the most dominant lesion(s) are contoured as GTVp_FB_post with the prefix 1, 2 etc. according to the number of lesions with the use of information from the planning MRI and PSMA-PET/CT used as guidance. As the lesions and the prostate gland normally decrease in size with neoadjuvant ADT, a CTVp_FB_final should be created. This volume should not only include the GTVp_FB_post but also account for the potential initial tumor volume (GTVp_FB_pre) as observed on the diagnostic MRI performed prior to initiating ADT. The three sequences used from mpMRI are:

- 1) T2 weighted image, where the tumour lesions appear in grey
- 2) DWI (Diffusion Weighted Imaging), where the tumour lesions appear as white areas
- 3) ADC (Apparent Diffusion Coefficient), where the tumour lesions appear as black areas

CTVp_FB should be included in the CTVp or CTVp_SV. No margin is used for intraprostatic lesions.

For radiation target nomenclature, see appendix C

Prostate: MRI is used to contour the CTVp volume as the whole gland with any visible extracapsular extension of disease included.

Elective pelvic lymph nodes: If N1, elective lymph nodes should be delineated according to NRG Oncology Updated International Consensus Atlas on Pelvic Lymph Node Volumes for Intact and Postoperative Prostate Cancer, 2021 (74). Elective pelvic lymph node area is named CTVn_E. Any clinically suspicious lymph nodes should be included in the CTVn_E. PTV is derived by adding a 5-10mm margin to CTVp, CTVp_SV and CTVn_E. See appendix D

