Seminal Vesicles (SV): If T3b disease, the entire seminal vesicle volume bilateral should be included in the CTVp_SV and treated to a high dose. If \leq T3a, only the proximal 2 cm of the seminal vesicle bilateral should be included in the CTVp_SV and treated to an elective dose. See appendix E

Organ at risk (OAR): will be contoured according to national guidelines.

Organs at risk

The prostate is situated adjacent to both the rectum and urinary system which risks gastro-intestinal (GI) and genitourinary (GU) adverse effects. The FLAME trial showed that long term side effects of conventional prostate RT even when combined with a mildly fractionated intra-prostatic boost are generally modest in frequency and severity (28). However, the addition of an extremely hypofractionated boost close to organs at risk approaches the realm of brachytherapy where very high point doses directly adjacent or even in the organ can lead to very severe adverse effects. The HypoFLAME trial (75) demonstrated that such an approach leads to only low frequencies of grade 2 side effects and very rarely grade 3. The results rely on the treatment being isotoxic i.e. maintaining pre-existing dose constraints of equivalent dose in the specific hypofractionated scheme. Table 1 in appendix B details the isotoxic dose constraints for the relevant organs at risk for each trial arm while Table 2 details the requirements for target coverage.

Study procedures

Identification and information of eligible patients

Eligible patients will be identified and discussed by doctors at the regional multidisciplinary team conference (MDT). Data from the medical record for eligibility screening are handed over to the researcher (name and CPR number of patients to receive radiotherapy, and diagnosis, i.e. cancer of the prostate/DC61.9). Other study relevant data are retrieved only after written consent. All patients

referred for RT who meet the inclusion criteria will be recorded on a screening list. Neoadjuvant and adjuvant ADT will follow Danish national guidelines, which currently include 3 months LHRH agonist or antagonist prior to the start of radiotherapy

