Subjects will accordingly to standard practice be followed for 10 years with a blood sample (PSA) monitoring disease control, whereas toxicity and quality of life (QoL) will be followed for 5 years. Testosterone is measured accordingly to local practice. Survival will be followed for up to 20 years. Additional visits beyond those established by the protocol will follow local guidelines. Protocol visits can be conducted by phone or video meeting, if preferred.

Data will be collected at follow-up visits as shown in the figure below

	Department of Urology 1. ADT	Department of Oncology Baseline Inclusion	Radiotherapy 20 fx 12 fx	3 months after start of RT 2. ADT	1 year 4. ADT	2 years 6. ADT	3 years	4 years	5 years	6-10 years
Months	-3	-1	0	3	15	27	39	51	63	75, 87, 99, 111, 123
Physical exam		x								
PSA	x	x		x	x	x	x	x	x	x
Testosterone*		(x)		(x)	(x)	(x)	(x)			
Biomarkers		x		x						
CTCAE		x		x	x	x			x	
PRO's and QoL		x		x	x	x			x	

* Recommended, but can be according to local practice

Toxicity registration

Gastrointestinal (GI) and genitourinary (GU) toxicities will be assessed according to Common Terminology Criteria for Adverse Events (CTCAE) v5.0. Acute toxicity is defined as adverse effects occurring within 90 days of the first radiation treatment, while late toxicity is defined as effects occurring 90 days or more after the first treatment. Toxicities will be analyzed in relation to dose-volume histograms (DVHs) for organs at risk (OARs), including the bladder, urethra, and rectum, as well as target structures, such as the gross tumor volume (GTV), clinical target volume (CTV), and planning target volume (PTV).

Patient-reported outcome measures (PROM) will include EORTC QLQ-PR25 and QLQ-C30.

PROM questionnaires will be sent to the patient's digital mailbox at predefined dates and to ensure a high response rate, the system will be configured to send automated reminders in case of missing responses. Data will be filed and stored using eCRFs in a REDCap database.

The data management system ensures compliance with current legislation and regulations on data handling and data safety. Sponsor, sponsor's representatives, investigators and controlling authorities have direct access to the above mentioned data including access to electronic patient records in order to ensure data quality and to monitor data quality.

Adverse Events (AEs) and Serious Adverse Events (SAEs)

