The potential advantages for a patient participating in the trial is to have fewer fractions in the experimental arms (12 fractions versus the standard arm of 20 fractions), and to reduce the risk of distant metastases by increasing the dose to the intraprostatic tumor lesion.

Potential risks for the patient

The potential disadvantage for the patient is an increased risk of late side effects from the lower urinary tract and rectum and bowel.

The side effects and risks of curatively intended combined LHRH-treatment, and radiotherapy for prostate cancer is well described and the patients will be informed about the risks before treatment.

We cannot exclude an increased risk of urinary and/or genito-urinary toxicity in the short treatment arm as the primary endpoint is non-inferiority for increased toxicity. A careful collection of recorded toxicity is therefore an important part of the study. An independent data monitoring committee will oversee the data during the study (see paragraph on independent data monitoring committee).

The concept of the study is to test if increased dose to intra prostatic lesions without increased dose to the surrounding organs improves tumour control. For the patients in the boost arm, we will also ensure that dose to urethra is kept the same dose level as the non-boost arm. However, we cannot completely exclude a higher risk of urinary toxicity.

Withdrawal of consent

The participant can withdraw from the trial at any time, and he does not have to give a reason for withdrawal. If he chooses to have standard therapy, this will be external beam radiotherapy according to the current DAPROCA guidelines.

Patients, who for some reason do not receive the allocated therapy, are to be treated at the doctor's discretion. The analysis of data will be according to the intention-to-treat principle. Unless the patient

does not accept it, he is followed as all other patients in the trial regarding the primary and secondary endpoints.

For patients not receiving the allocated therapy or withdrawing from the trial at a later point of time, the date of exit from the trial is registered as also the reason if possible. The patient is informed about the burden of follow up before randomization to minimize withdrawal from the trial. The patient can withdraw from the trial without telling a reason at any time.

Possible benefits for society

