Appendix B: Dose constraints

Table 1 below shows isotoxic dose constraints to organs at risk. The Equivalent Dose at 2 Gy fractions known from the conventional 39-fraction treatment regime have been converted to equivalent doses for the two hypo-fractionated schemes using an α/β -value of 3.

Requirements for target coverage for the two hypo-fractionated schemes are listed in table 2. Both tables include priorities designating in which order specific constraints should be fulfilled in case of conflicts between target and OAR. CTVs and certain OARs both have priority 1. This should not lead to conflicts since there are no overlaps between the two.

Table 1

OAR	Normo-fractionated DVH constraint	EQD2 of physical dose	Isotoxic dose: 20 fractions ($\alpha/\beta = 3$)	Isotoxic dose: 12 fractions ($\alpha/\beta = 3$)	Priority
Rectum	$V_{75\text{Gy}} < 2\text{cm}^3$	74 Gy	60 Gy	50 Gy	1
	$V_{70\text{Gy}} < 10\%$	67 Gy	55 Gy	46 Gy	3
	$V_{50\text{Gy}} < 60\%$	43 Gy	46 Gy	31 Gy	3
Urethra	$D_{0.1\text{ccm}} < 85\text{Gy}$	88 Gy	71 Gy	59 Gy	1
	$D_{1\text{ccm}} < 80\text{Gy}$	81 Gy	65 Gy	54 Gy	1
Bowel Bag	$D_{\text{max}} < 78\text{Gy}$	78 Gy	63 Gy	53 Gy	1
Bowel Bag - PTV_5mm	$V_{30\text{Gy}} < 450\text{cm}^3$	23 Gy	20 Gy	18 Gy	3
	$V_{45\text{Gy}} < 195\text{cm}^3$	37 Gy	32 Gy	28 Gy	3
Bladder	$D_{\text{mean}} < 62\text{Gy}$	57 Gy	47 Gy	40 Gy	3
	$V_{80\text{Gy}} < 15\%$	81 Gy	65 Gy	54 Gy	3
	$V_{70\text{Gy}} < 35\%$	67 Gy	55 Gy	46 Gy	3
Femoral Heads	$D_{2\%} < 55\text{Gy}$	48 Gy	41 Gy	35 Gy	3
Body (outside PTVs)	$D_{2\%} < 83\text{Gy}$	85 Gy	67 Gy	56 Gy	3

Table 2

Target volume (X denoting specific dose scheme)	DVH constraint		Priority
	20 fractions	12 fractions	
GTVp_FB_post_X	$D_{\text{mean}} = 75 \text{ Gy} (\pm 1\%)$	$D_{\text{mean}} = 60 \text{ Gy} (\pm 1\%)$	2
GTVp_FB_post_X	$V_{71.25\text{Gy}} > 99.5\%$	$V_{57\text{Gy}} > 99.5\%$	2
CTVp_FB_final_X	$V_{71.25\text{Gy}} > 95\%$	$V_{57\text{Gy}} > 95\%$	3
CTVp_FB_final_X	$D_{0.1\text{ccm}} > 80.25\text{Gy}$	$D_{0.1\text{ccm}} > 64.2 \text{ Gy}$	3
CTVp_X	$V_{57\text{Gy}} > 99.5\%$	$V_{47.5\text{Gy}} > 99.5\%$	1
CTVp_SV_X (T3b)	$V_{57\text{Gy}} > 99.5\%$	$V_{47.5\text{Gy}} > 99.5\%$	1
CTVp_SV_X ($\leq T3a$)	$V_{42.75\text{Gy}} > 99.5\%$	$V_{35.15\text{Gy}} > 99.5\%$	1
CTVn_E_X	$V_{42.75\text{Gy}} > 99.5\%$	$V_{35.15\text{Gy}} > 99.5\%$	1
PTVp_X	$V_{57\text{Gy}} > 98\%$	$V_{47.5\text{Gy}} > 98\%$	2
PTV_SV_X (T3b)	$V_{57\text{Gy}} > 98\%$	$V_{47.5\text{Gy}} > 98\%$	2

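### The contouring rule sends every organ at risk to the planning CT and does not except the urethra, although the boost lesion and the surrounding prostate are drawn on the planning MRI

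*Protocol*

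**What the plan says.** All references are to the protocol.

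- **Target volume definition, dose and fractionation.** Targets are drawn on the treatment planning MRI, guided by the diagnostic MRI and the PSMA-PET/CT. The next sentence reads "Organs at risk (OARs) are delineated on the planning CT scan". For the prostate, "MRI is used to contour the CTVp volume as the whole gland". The intraprostatic lesion gets no margin. At the end of the same section: "Organ at risk (OAR): will be contoured according to national guidelines".
- **Toxicity registration.** The urethra is named among the "organs at risk (OARs), including the bladder, urethra, and rectum".
- **Appendix B, Table 1.** The urethra has two limits, both priority 1: D0.1ccm below 85 Gy and D1ccm below 80 Gy in the conventional schedule, with converted values for 20 and 12 fractions. In Table 2, boost dose to the lesion is priority 2, and coverage of the final boost volume is priority 3.
- **Potential risks for the patient.** For the boost arm, "we will also ensure that dose to urethra is kept the same dose level as the non-boost arm".
- **Increased dose to intra-prostatic cancer lesions.** FLAME data are said to suggest less toxicity through attention to organ-at-risk dose and "improved urethral sparing in particular".
- **Appendix A, Delineation and dose planning quality assurance.** A workshop is to produce consensus guidelines for target and organ-at-risk delineation. Their content is not given.

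**The concern.** Most organs at risk lie beside the prostate. The urethra runs through it, close to or possibly against the boosted lesion. The general rule therefore puts two neighbouring structures in one organ on two different image sets: the lesion on MRI and the urethra on CT. Their planned separation is what the Table 1 urethra check tests.

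The protocol itself explains why that separation matters. Radiotherapy planning describes sharp dose gradients towards organs at risk. Organs at risk warns of severe harm from very high point doses next to or inside an organ, and says the cited safety results rely on keeping the dose constraints. D0.1ccm is close to a point-dose limit, so it is sensitive to where the contour lies.

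An error could act in either direction. A urethra contour placed too far from the boost can hide an overdose, and the promise on urethral dose would then appear to be kept when it is not. A contour placed too near the boost, or inside it, can cost boost dose needlessly, because the urethra outranks boost coverage.

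**Working it through.** The protocol gives no figure to reproduce here. The check is a comparison of texts, followed by a short error argument.

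**1. Is there an exception elsewhere?** The urethra is mentioned in five places: the background on focal boost, the late-toxicity dose-response section, Toxicity registration, Potential risks for the patient, and Table 1. None says on which image it is contoured. The reference to national guidelines names no image set. The consensus guideline is still to be written.

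**2. What follows if the rule is taken as written?** Let *l* be the contour error for the lesion on MRI, *r* the MRI-to-CT registration error, *c* the contour error for the urethra on CT, and *m* the contour error for the urethra on MRI. The error in the planned boost-to-urethra separation is:

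- Urethra on CT: (*l* + *r*) − *c*
- Urethra on MRI, transferred with the targets by the same registration: (*l* + *r*) − (*m* + *r*) = *l* − *m*

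With both structures on the MRI, the registration term cancels from their separation. It remains in their common position on the CT, where MRI-drawn targets already carry it. This step does not depend on how well CT shows the urethra. It also does not show that *m* is smaller than *c*; the protocol gives no value for either. The nearest statement, under Imaging, is that MRI improves the accuracy of prostate delineation.

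**3. Does the protocol handle CT-MRI differences for other structures?** Yes. Appendix C bases the involved seminal vesicles on MRI and adjusts them to their location on CT. Appendix E draws the vesicles on both scans and combines the volumes. The urethra gets no comparable instruction. Appendix B also says that priority-1 CTVs and organs at risk do not overlap. That cannot be true of a urethra inside a whole-gland CTV, which suggests that the general rules were written without the urethra in mind.

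**4. Size.** No contour error, registration error or dose gradient is given, so neither a displacement in millimetres nor a dose error in Gy can be derived. Only the reach can be stated. With "254 patients in each of the four arms for a total of 1,016 patients", the two boost arms hold 2 × 254 = 508 patients to whom the promise on urethral dose applies. This is not a count of patients with a wrong contour.

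**5. Why boost dose is not compared with the urethra limit.** With EQD2 = D(D/n + 3)/5, 85 Gy in 39 fractions gives 85 × (2.18 + 3)/5 = 88.1 Gy, matching the 88 Gy in Table 1. The listed equivalents give 71 × (3.55 + 3)/5 = 93.0 Gy in 20 fractions and 59 × (4.92 + 3)/5 = 93.4 Gy in 12. That mismatch is a separate matter. The present point does not rely on those limits.

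**The case against.** The strongest reply is that the sentence is only a general summary. Delegating organ contouring to a national guideline is ordinary practice, and the protocol does so in the same section. The consensus workshop will use a dataset that includes MRI, and the seminal vesicle guidance shows that structure-specific instructions refine the general rule. A contour held on the planning CT but guided by MRI would fit all these texts.

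Much of this stands. A reader might infer that centres will contour the urethra on CT alone. The documents do not support that, because both guidelines are unseen and either may specify MRI. What does not fall away is the sentence itself. It states a rule without exception, and a centre following it literally would use CT. If a guideline says otherwise, the protocol should agree with it.

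A reader might also rest the case on poor visibility of the urethra on plain CT. The protocol does not say this, and the registration argument does not need it.

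Finally, a reader might take the limited central review in Appendix A, which covers the first boost patient in each fractionation regimen at each centre, as a measure of the problem. It measures how many contours are sampled, not how many are wrong, and it would be the same with the urethra drawn on MRI. That review could also reveal a systematic local practice early.

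**Conclusion.** The point holds as a minor patient-safety improvement. The protocol's stated rule, if followed, makes the boost-to-urethra distance depend on registration between two scans and on a CT contour of an intraprostatic structure. The Table 1 urethra check, which supports the promise on urethral dose, is then less reliable than it could be at almost no cost.

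This rests on two assumptions: that the unseen guidelines do not already resolve the matter in practice, and that MRI-drawn structures are transferred together by one registration. If the guidelines do specify MRI, what remains is an inconsistency of wording. The size of the error is unknown.

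A reader might infer bias in the trial's results. The documents do not support it: the randomised comparisons of toxicity and of freedom from distant metastasis compare patients as allocated, and neither endpoint is measured from this contour. The planned urethral dose-response analysis would be affected only where clinical contours are used, since automated segmentation is also foreseen.

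**What to change.** In Target volume definition, dose and fractionation, and in the consensus guideline, state that organs at risk are delineated on the planning CT except the urethra, which is contoured on the planning MRI in all four arms and transferred to the planning CT with the targets. Using one method in all arms keeps the comparison with the non-boost level like for like. If the national guideline already says this, cite it at that sentence so that the texts agree. Use this contour for the Table 1 check and, where clinical contours are used, for the dose-response analysis.

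The cost is one sentence in each document and slightly more contouring time. No new scan is needed: targets are already drawn on the planning MRI, and patients who cannot have an MRI are excluded. The contour would carry the registration uncertainty that MRI-drawn targets already carry. Artefacts around the gold markers, which Imaging quality assurance still plans to quantify, may also affect it.

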Appendix C: Radiation target nomenclature

Target	Delineation	GTV nomenclature	CTV nomenclature	PTV According to local guidelines	Doses	Number of fractions
Intraprostatic lesion(s) if boost is performed (prior to initiating ADT)	Based on MRI +/- PSMA-PET CT signals	GTVp1_FB_pre* GTVp2_FB_pre* etc.	N/A	N/A	N/A	N/A
Intraprostatic lesion(s) if boost is performed (post initiating ADT)	Based on MRI +/- PSMA-PET CT signals	GTVp1_FB_post_75 GTVp2_FB_post_75 etc. GTVp1_FB_post_60 GTVp2_FB_post_60 etc.	CTVp1_FB_final_75 CTVp2_FB_final_75 etc. CTVp1_FB_final_60 CTVp2_FB_final_60 etc.	N/A	75 Gy 60 Gy	20 fx 12 fx
Prostate	MRI used for volume definition		CTVp_60 CTVp_50	PTVp_60 PTVp_50	60 Gy 50 Gy	20 fx 12 fx
Seminal Vesicles - if invasion (T3b)	Based on the MRI and adjusted according to location on the CT scan		CTVp_SV_60 CTVp_SV_50	PTVp_SV_60 CTVp_SV_50	60 Gy 50 Gy	20 fx 12 fx
Seminal Vesicles - no invasion (≤ T3a)	The proximal 2 cm of vesicles		CTVp_SV_45 CTVp_SV_37	PTVp_SV_45 PTVp_SV_37	45 Gy 37 Gy	20 fx 12 fx
Elective pelvic lymph nodes	According to NRG Oncology Updated International Consensus Atlas on Pelvic Lymph Node Volumes		CTVn_E_45 CTVn_E_37	PTVn_E_45 PTVn_E_37	45 Gy 37 Gy	20 fx 12 fx

Abbreviations: GTV: Gross Tumour Volume; CTV: Clinical Target Volume; PTV: Planning Target Volume; Gy: Gray; fx: Fractions

* There are no dose constraints for the GTV(s) defined prior to initiating ADT. This/these volume(s) should be included in the CTV(s) for the intraprostatic lesion(s).

[figure not shown]

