Appendix E: Guideline for seminal vesicle radiotherapy

Radiotherapy to the seminal vesicles are being performed quite differently throughout Denmark. The DAPROCA10 core group suggests the below strategy to be used in the trial for consistency and improved outcomes of the trial, where precision of the radiotherapy is a key factor. Imaging of seminal vesicle involvement (SVI) is optimally performed with a combination of multiparametric MRI and PSMA PET/CT and the proposed strategy is dependent on the use of contemporary prostate cancer imaging. SVI rarely occurs without the involvement of the “midbase” of the prostate gland, as the cancer spreads along the ejaculatory ducts or as extraprostatic extension into the seminal vesicles. In a study of prostate cancer specimens, the percentage of seminal vesicle invasion with and without “midbase” invasion was 78% and 0.7%, respectively (93,94).

[figure not shown]
Pattern of spread- Ohori’s classification

In an often referred publication from Kestin et al the median length of SVI was 1 cm with a 90% percentile of 2 cm, forming the basis for including the proximal 2 cm of the seminal vesicles as an elective target (95).

Below are three examples illustrating when and how the seminal vesicles are to be included as a target.

No elective irradiation of seminal vesicles

[figure not shown]

Tumour does not involve base of prostate gland

Little risk of SVI

No elective SV volume

[figure not shown]
Elective irradiation of seminal vesicles

Tumour involves base of prostate gland

Include proximal 2 cm of seminal vesicles bilaterally as elective target

Irradiation of seminal vesicles

Tumour involves left SV on MRI/PET

[figure not shown]
Include GTV of involved seminal vesicle in focal boost volume if randomised for boost

The remaining SV volume included in 50 or 60 Gy volume

Contouring of seminal vesicles

Delineate CTV SV on both planning CT (blue) and MRI (red)

Create ITV SV from the sum of both volumes (yellow) and subtract the part of the ITV SV extending into rectum (brown)

References

1. de Crevoisier R, Bayar MA, Pommier P, Muracciole X, Pêne F, Dudouet P, et al. Daily Versus Weekly Prostate Cancer Image Guided Radiation Therapy: Phase 3 Multicenter Randomized Trial. *Int J Radiat Oncol Biol Phys.* 2018;102(5):1420–9.

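### The protocol gives three conflicting rules for seminal vesicle dose in tumours of stage T3a or less; the first two differ by about 25 to 27 Gy EQD2 in prescribed dose

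*Protocol*

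**What the plan says.** Four places in the protocol deal with seminal vesicle dose.

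- **Per-arm list (Target volume definition, dose and fractionation).** "20 fractions, no boost: Prostate and seminal vesicles: 60 Gy/ 20 fractions" and "12 fractions, no boost: Prostate and seminal vesicles: 50 Gy/ 12 fractions, Pelvic: 37 Gy /12 fractions". The two boost arms repeat these vesicle doses. No line carries a stage condition.
- **Seminal vesicle paragraph, same section.** "If T3b disease, the entire seminal vesicle volume bilateral should be included in the CTVp_SV and treated to a high dose". At T3a or less, "only the proximal 2 cm of the seminal vesicle bilateral should be included in the CTVp_SV and treated to an elective dose". There is no condition on involvement of the prostate base. The paragraph ends by referring to Appendix E.
- **Appendices B and C.** Appendix C names the T3a-or-less volumes "CTVp_SV_45 CTVp_SV_37", at 45 Gy in 20 fractions and 37 Gy in 12. Appendix B, Table 2, sets the matching coverage goals (42.75 and 35.15 Gy) at priority 1.
- **Appendix E.** This divides patients by tumour location. If the base is not involved: "No elective SV volume". If the base is involved: "Include proximal 2 cm of seminal vesicles bilaterally as elective target". If a vesicle is involved: "The remaining SV volume included in 50 or 60 Gy volume".

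**The concern.** The list, the stage rule and the location rule do not give the same instruction for tumours of stage T3a or less. A planner who works from the list treats the vesicles to the prostate dose. One who works from the stage rule treats the proximal 2 cm to the elective dose. One who works from Appendix E may draw no vesicle target at all.

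Two things are at stake. The first is safety: the vesicles lie next to the rectum, as Appendix E acknowledges by cropping the vesicle volume where it extends into the rectum. The second is what the trial measures. Grade 2 or worse GI and GU toxicity are the endpoints of the fractionation comparison, with reference rates of 10% and 20% and boundaries of 15% and 27%. If centres follow different passages, one arm label covers different treatments, and the toxicity rates carry variation that could have been avoided. Appendix E itself reports that Danish practice on the vesicles varies widely and offers its strategy for the sake of consistency.

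**Working it through.** **1. The rules by patient type**

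| Patient | Per-arm list | Seminal vesicle paragraph, Appendices B and C | Appendix E |
|---|---|---|---|
| T3b | 60 or 50 Gy | Entire vesicles, 60 or 50 Gy | 60 or 50 Gy (involved part in the boost volume if randomised to boost) |
| T3a or less, base involved | 60 or 50 Gy | Proximal 2 cm, 45 or 37 Gy | Proximal 2 cm, elective |
| T3a or less, base not involved | 60 or 50 Gy | Proximal 2 cm, 45 or 37 Gy | No volume |

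For T3b the sources agree on the dose level. With T3a or less and base involvement, only the list differs. With T3a or less and no base involvement, all three differ.

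**2. The protocol's own EQD2 figures**

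The design table under Statistical considerations gives 77 Gy for 60 Gy/20, 48 Gy for 45 Gy/20, 80 Gy for 50 Gy/12 and 48 Gy for 37 Gy/12. It states no alpha/beta. The formula is EQD2 = D × (D/n + α/β) / (2 + α/β). With α/β = 1.6:

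- 60 × (3.00 + 1.6)/3.6 = 76.7
- 45 × (2.25 + 1.6)/3.6 = 48.1
- 50 × (4.167 + 1.6)/3.6 = 80.1
- 37 × (3.083 + 1.6)/3.6 = 48.1

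The four figures are reproduced. The value 1.6 is inferred from this fit. On the tabulated figures, the gap between prostate level and elective level is 77 − 48 = 29 Gy in 20 fractions and 80 − 48 = 32 Gy in 12.

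**3. The same gap at the organ-at-risk value**

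Appendix B uses α/β = 3 for organs at risk:

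- 60 Gy/20: 60 × 6.00/5 = 72.0
- 45 Gy/20: 45 × 5.25/5 = 47.25
- 50 Gy/12: 50 × 7.167/5 = 71.7
- 37 Gy/12: 37 × 6.083/5 = 45.0

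The gaps are 24.8 Gy (20 fractions) and 26.7 Gy (12 fractions).

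**4. Sensitivity**

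| α/β | Gap, 20 fractions | Gap, 12 fractions |
|---|---|---|
| 1.5 | 28.9 Gy | 32.5 Gy |
| 3 | 24.8 Gy | 26.7 Gy |
| 5 (not used in the protocol) | 22.0 Gy | 22.8 Gy |

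**5. Against the no-volume case**

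Here the whole prescription is in question: about 72 Gy EQD2 at α/β = 3 if compared with the list, and 47.25 or 45.0 Gy if compared with the elective rule. The dose that an untargeted vesicle would actually receive depends on the plan, and the protocol does not give it.

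**The case against.** The best reply is that the list is a one-line summary for each arm, and that the seminal vesicle paragraph and Appendices B and C refine it consistently. Plans must meet Appendix B, and Appendix C offers no 60 or 50 Gy structure for T3a or less. This is a reasonable reading, but the list states no condition. Even if it is granted, the stage rule still conflicts with Appendix E for tumours that spare the base: neither the paragraph nor the priority 1 row of Table 2 has a base condition.

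Appendix E can also be called advice, since it is worded as a suggestion. The same appendix, however, presents its examples as showing when and how the vesicles are to be targeted. The seminal vesicle paragraph points to it, and Treatment related procedures requires contouring by the protocol's own guidelines. If it is optional, the protocol permits two practices.

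A third reply is that other safeguards limit the harm: organ constraints, a delineation workshop and quality assurance review. They do so only in part.

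- In Appendix B, one rectal constraint has priority 1. The other rectal constraints and all bladder constraints have priority 3, below the priority 1 vesicle volume.
- Patient-level review in Appendix A covers the first boost patient in each schedule at each centre, two in all. It describes no such review of no-boost patients.

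Three points on the other side stand. T3b is unaffected. The EQD2 gap is in prescribed vesicle dose and cannot be read as rectal dose, which is constrained separately. The ambiguity is identical in all four arms and randomisation is stratified by centre, so it does not by itself bias either comparison.

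**Conclusion.** The concern holds. For stage T3a or less the protocol contradicts itself on whether the vesicles are treated to the prostate dose or the elective dose. Where the base is also spared, it contradicts itself on whether they are a target at all. The prescribed difference between the first two rules is 24.8 Gy EQD2 in 20 fractions and 26.7 Gy in 12 at α/β = 3, or 29 and 32 Gy on the protocol's own tabulated figures.

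The consequence is avoidable variation in treatment within each arm and a patient-safety issue. No bias between arms is claimed, and no effect on GI or GU rates can be calculated from the document. The share of patients at T3a or less without base involvement is not given, so the number exposed to the full three-way conflict is unknown. The Appendix E cases accompany figures that are not reproduced in the text reviewed, so any stage labels in them could not be checked.

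**What to change.** Reconcile the per-arm list, the seminal vesicle paragraph, Appendix B Table 2, Appendix C and Appendix E, so that one rule for vesicle volume and dose appears everywhere. It should state every condition it depends on (stage, base involvement or both) and apply equally in all four arms. State also whether Appendix E is binding. Which rule is right is for the sponsor's clinicians to decide; this review takes no position.

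The cost is a text correction, to be made before sites plan patients. It does not affect the sample size.
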